המרכז הרפואי תל-אביב
ע"ש סוראסקי
רפואה מובילה ואנושית

Proposed Study Title

Study Title

Performance Evaluation Protocol for Sight Diagnostics' OLO CBC Analyzer by Ichilov oncology daily care center.

Contact Information

Name

[name]

Job Title

VP R&D

Institution

Sight Diagnostics

Address 1

[name]

Address 2

City, State, Zip

Tel Aviv

Country

Israel

Phone/Fax

E-mail	[contact]
--------	--------------------

Study Information

Tumor Type	N/A				
Areas of Interest	N/A				
# of Patients	50	Study Duration (Months)	1	Number of Sites	1
Site Names	Sight Diagnostics				

Hypothesis / Overall Objectives

Background:

The Sight OLO is a quantitative multi-parameter automated hematology analyzer intended for in vitro diagnostic use in screening capillary or venous whole blood samples collected in K₂EDTA blood collection tubes, or fingertip samples collected using the Sight OLO test kit microcapillary tubes. When used with the Sight OLO cartridge, the Sight OLO enumerates the following CBC parameters in whole blood: WBC, RBC, HGB, HCT, MCV, MCH, MCHC, RDW, PLT, NEUT%/#, LYMPH %/#, MONO %/#, EOS%/#, and BASO%/#.

The Sight OLO is indicated for use in point of care and clinical laboratories to identify and classify one or more of the formed elements of blood in children 3 months and above, adolescents and adults. In case a different intended use is required by the evaluating site, Sight should be informed in advance.

As there are great benefits in performing CBC tests from fingertip in oncologic patients, this study aims to establish OLO’s performance accuracy of CBC results for finger prick samples across the OLO reportable range, and particularly around relevant medical decision points. Additionally, the study will evaluate OLO’s compatibility to Ichilov oncology daily care center, while focusing on its effect of workflow and turnaround time.

Hypothesis:

The results of this study are expected to show good performance of OLO and its equivalence to the site's standard hematology system - Beckman Coulter DxH800 analyzer - in samples spanned over a wide clinical measuring range and covering medical decision points for WBC, HGB, PLT, and NEUT#. The medical decisions taken for treating chemotherapy patients at the oncology center are expected to remain equal when based on the results given by Sight OLO.

OLO is hypothesized to allow shorter time to CBC results, by minimizing the time period from phlebotomy to results, currently prolonged due to the need to send blood samples from the oncology

daily care center to the central lab. By that, Sight OLO would improve workflow efficiency and provide care to patients in a reliable and accelerated fashion.

Study Description

Provide a concise overview stating the type of study, phase, design, and compounds

Study design:

This evaluation will include two studies:

1. A matrix study will compare a capillary sample collected via finger prick with a venous sample collected into a blood tube, both scanned on OLO.
2. A method comparison study will compare Sight OLO to Beckman Coulter DxH800 using a venous sample collected into a blood tube.

During a period of 2 weeks, approximately 50 whole blood samples will be collected from patients at the oncology daily care center.

Patient Enrollment:

- Each patient participating in the study will firstly fill and sign an Informed Consent Form (ICF). Subjects participating in the study will be rewarded with a coupon for coffee and cake.
- For de-identification purposes, study barcode stickers will be used for all of OLO scans, instead of the original patient identification details. An unblinded form will be used to match the de-identification barcode with the patient identification details (this form will remain at the center and will not be shared externally).
- Patient enrollment will be documented in a designated worksheet, using the study barcode stickers.
- The patient will be asked to rest for at least 15 minutes.

Phlebotomy and Scanning Flow:

During the routine blood collection, an additional venous sample will be collected in K₃EDTA tube as part of the study. The phlebotomy time will be recorded in the worksheet.

The first tube will get a study barcode sticker and remain in the daily care center at a room temperature of 18°C-26°C. The second tube will be sent to the lab to be scanned on Beckman Coulter DxH800, as part of the routine procedure.

Two consecutive finger prick samples will be collected from the 3rd and 4th fingers of the patient's non-dominant hand (in this order) and scanned on OLO, and the time of the first result will be recorded in the study worksheet.

Following two successful finger prick scans, the venous sample (collected previously for the study) will be scanned on OLO.

The following time points will be recorded in the study worksheet:

- Phlebotomy time
- Scanning time on the reference device at the lab.

This study design is illustrated in the study scheme below.

Study Requirements:

- All four scans will be performed within no more than 2 hours.
- All scans should be performed within 8 hours from phlebotomy.
- Venous samples should be collected in K₃EDTA tubes with a minimum volume of 700µL and kept at room temperature of 18°C-26°C throughout the day until the last scan is completed.
- The finger prick samples will be collected using lancets provided by Sight.
- If a finger prick scan is rejected, another sample will be collected from another finger, in the following order: non-dominant 3rd -> non-dominant 4th -> dominant 3rd -> dominant 4th. Up to 4 finger prick attempts will be performed **in total** for the two finger prick scans. If less than 2 finger prick scans are completed successfully, the sample should be excluded from the study. For each successful scan, the corresponding finger will be recorded in the worksheets.
- In case any of the venous scans are rejected, an additional repeat should be performed. Up to 3 attempts will be performed for each sample, and in case a 3rd failure occurs, the sample should be excluded from the study.
- Only 1 reference device should be used throughout this study - Beckman Coulter DxH800.
- A single operator will participate in the study.
- All relevant documents, including forms, worksheet and barcode stickers will be provided by Sight.

Primary endpoint:

Following the initial period of 2 weeks in which the samples will be randomly selected, the results will be evaluated to assess the coverage of the predefined range groups (specified in the study population section), in order to understand the timeframe and the type and quantity of samples required for completion of the study. If needed, a purposeful method for samples collection will be used, according to the missing ranges.

Purposeful Sampling Method - Study Design: A sample will be enrolled according to the result received from the routine CBC test from the same day (on Beckman Coulter DxH800) and incomplete range groups (specified in table 1). Once enrolled in the study, the samples collection and scanning will be performed in the same order as in the initial phase (illustrated in the study scheme below). During the purposeful method, the time to results will not be included in the analysis.

Secondary endpoint:

Once all the predefined range groups are covered, the study will be completed and the results will be analyzed.

Statistical considerations:

Passing Bablok regression analyses will be performed for each measurand between:

- (1) The mean value given by OLO for the finger prick samples and the value given by OLO for the venous sample.

- (2) The value given by OLO for the venous sample and the value given by Beckman Coulter DxH800 for the venous sample.

Measurands invalidated by either OLO or Beckman Coulter DxH800 will be removed from all analyses.

The time to result will be compared between the time of first available finger prick results (from the scan on OLO) and the time of available venous results (from the routine scan on Beckman Coulter).

After study completion, medical records of the enrolled patients will be reviewed to evaluate whether the same clinical decision would have been taken when based on OLO results.

Environmental requirements:

- OLO should be placed on a stable bench (shared with no vibrating equipment) with enough space for the device and an adjacent surface for sample preparation. OLO's physical measurements are: 25.7X32.6X28.7 cm, 10 kg.
- Power supply - OLO is provided with a power supply unit which needs to be connected to a standard grounded power socket.
- Internet connectivity - not mandatory for operation but preferable for remote support and monitoring. LAN connectivity is preferable. Sight can provide 3G/4G dongle for cellular connectivity. It would be best to contact an IT person directly to understand whether there are special compliance requirements when connecting OLO to the local network/internet.
- Each blood tube should be kept at room temperature of 18°C-26°C throughout the day until the last scan is completed. The OLO operating temperature range is 18°C-30°C, relative humidity range is 20%-80%.
- The reference device must be calibrated and approved for use according to the lab standard operating procedures during the entire performance evaluation study. If any calibration process is performed during the study, Sight should be informed, preferably in advance, to be able to take the steps required to avoid interference with the method comparison (such as the removal of the samples scanned before/after the calibration).
- Results from the OLO can be exported as a CSV file through a USB drive and sent via email.

Sharing of results:

- Given this is an early comparison study, results will be shared openly across both parties.
- CSV files with the results of OLO and de-identified PDF files with the results of the reference device should be shared regularly by the study coordinator.
- Study worksheets and enrollment forms will be delivered once completely filled.

Study Population

Brief description, setting and key inclusion/exclusion criteria

Inclusion Criteria:

Blood samples will be collected from oncologic patients older than 18 years old arriving at the oncologic daily care center of Ichilov hospital.

The sampling method will initially be randomized, though will aim to include both normal and abnormal ranges of blood counts (according to Beckman Coulter DxH800 as the reference analyzer), while covering wide analytical ranges with balanced distributions, focusing on values around medical decision points. Approximately 30 abnormal samples will be collected, with the ranges to cover specified in table 1 below. Note that a single sample can cover multiple ranges for different parameters. Additionally, approximately 20 normal samples will be collected, while for the purpose of this protocol, normal is defined as samples with values above the ranges specified in table 1 for all parameters (PLT>100X10³/μL, HGB>12.0g/dL, WBC>4.0X10³/μL, NEUT#>2.0X10³/μL), and with no flags on the site reference analyzer.

Table 1 - abnormal ranges

[figure not shown]
	Range	# of paired samples
PLT	<100X10 ³ /μL and >50X10 ³ /μL	2
	<50X10 ³ /μL and >30X10 ³ /μL	4
	<30X10 ³ /μL and >18X10 ³ /μL	4
	<18X10 ³ /μL	4
HGB	<12.0g/dL and >10.0g/dL	4
	<10.0g/dL and >4.0g/dL	4
WBC	<4.0X10 ³ /μL and >2.0X10 ³ /μL	2
	<2.0X10 ³ /μL	7
NEUT#	<2.0X10 ³ /μL and >1.0X10 ³ /μL	3
	<1.0X10 ³ /μL and >0.5X10 ³ /μL	3
	<0.5X10 ³ /μL	2

Exclusion Criteria:

- Visibly hemolyzed specimens (sample plasma should be checked for hemolysis by technician while selection of specimen from tube racks).
- Visibly clotted specimens (Reasonable to assume that samples processed with clinical reported results are not clotted).
- A sample that is not successfully scanned on OLO within 3 attempts (e.g. rejected due to irregular cell morphology, or microscopically visible hemolysis).

Study Schema

Please insert a graphic study schema or visual representation of trial design

Protocol revision signatures: This study protocol has been reviewed by Sight's key personnel with their signature approval for its use.

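### Entry to the venous OLO-versus-DxH800 comparison depends on two successful finger pricks, although that comparison uses no finger prick value

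*Protocol*

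**What the plan says.** All references are to the Protocol.

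- **Study design** names two studies. The second is purely venous: "A method comparison study will compare Sight OLO to Beckman Coulter DxH800 using a venous sample collected into a blood tube".
- **Statistical considerations** matches this. The second Passing-Bablok regression is between "The value given by OLO for the venous sample and the value given by Beckman Coulter DxH800 for the venous sample". The finger prick mean enters only the first regression.
- **Phlebotomy and Scanning Flow** has both venous tubes taken before any prick. For the study tube: "During the routine blood collection, an additional venous sample will be collected in K₃EDTA tube as part of the study". For the routine tube: "The second tube will be sent to the lab to be scanned on Beckman Coulter DxH800, as part of the routine procedure".
- The same section then sets the condition for running the study tube on OLO: "Following two successful finger prick scans, the venous sample (collected previously for the study) will be scanned on OLO".
- **Study Requirements** allows at most four pricks, one per finger, in the order "non-dominant 3rd -> non-dominant 4th -> dominant 3rd -> dominant 4th". It adds: "If less than 2 finger prick scans are completed successfully, the sample should be excluded from the study". Venous scans have their own failure rule of up to three attempts.
- The purposeful sampling phase, described under **Primary endpoint**, keeps the same collection and scanning order. The condition therefore also applies while the scarce Table 1 ranges are being filled.
- Under **Secondary endpoint**, the study ends only when all range groups are covered.

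**The concern.** The second regression carries the hypothesis that OLO is equivalent to the site's DxH800. It needs two venous results per patient, and both tubes exist by the time the pricks fail. The protocol nevertheless makes the OLO venous scan depend on a different specimen type, and it words the exclusion as leaving the study rather than leaving the matrix comparison.

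Three consequences follow:

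- A patient whose capillary collection failed but whose venous blood OLO could read is lost from a comparison that did not need the finger prick.
- The method comparison describes only patients whose capillary samples OLO accepted twice, a filter with no role in a venous comparison.
- With the tube unscanned, the study cannot show whether a finger prick failure came from collection or from the blood.

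The value is never generated, so no later analysis plan can restore it.

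**Working it through.** **1. Which data each regression needs**

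| | Finger prick values | OLO venous | DxH800 venous |
|---|---|---|---|
| Regression 1 (matrix) | mean of two | yes | no |
| Regression 2 (method comparison) | none | yes | yes |

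Only regression 1 needs two successful pricks. The exclusion in Study Requirements removes the patient from both.

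**2. Who is lost**

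Patients with 0 or 1 successes in four attempts are lost. A patient with one or two rejected pricks who still reaches two successes is kept.

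**3. Planned number**

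Inclusion Criteria gives about 30 abnormal and about 20 normal samples: 30 + 20 = 50, which agrees with Study design. The protocol states no rejection rate.

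**4. Size of the loss, over an assumed range**

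Let r be the rejection probability per prick (an assumption), independent between pricks. With at most four pricks:

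P(excluded) = P(fewer than 2 successes) = 4r³(1 − r) + r⁴

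| r | 4r³(1 − r) | r⁴ | P(excluded) | Expected loss of 50 |
|---|---|---|---|---|
| 0.10 | 0.0036 | 0.0001 | 0.0037 | 0.2 |
| 0.20 | 0.0256 | 0.0016 | 0.0272 | 1.4 |
| 0.30 | 0.0756 | 0.0081 | 0.0837 | 4.2 |
| 0.40 | 0.1536 | 0.0256 | 0.1792 | 9.0 |

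**5. Effect of clustering (illustrative assumption)**

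Keep the mean rejection rate at 10%, but let 10% of patients reject at 80% and the rest at about 2.2% (0.10 × 0.80 + 0.90 × 0.022 ≈ 0.10).

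- For the difficult patients, P(excluded) = 4 × 0.8³ × 0.2 + 0.8⁴ = 0.4096 + 0.4096 = 0.819.
- For the others it is about 0.00004.
- Overall it is about 0.10 × 0.819 ≈ 0.082, or 4.1 of 50. This is roughly 22 times the independent case (0.082 / 0.0037), and nearly all of it falls on the difficult patients.

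**6. Replacement**

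Enrolment runs until the range groups are covered, so a lost sample leaves its Table 1 cell open and another patient fills it. The figures above therefore measure patients discarded and the strength of the filter. They do not measure a deficit in the final number of pairs.

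**The case against.** **Numbers are replaced.** This stands. It would be wrong to treat the Table 1 counts as a fixed cohort and to compute the chance that a cell falls short, because they are quotas. Replacement restores the count but not the kind of patient lost, and each replacement means another patient's draw and pricks.

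**The effect may be tiny.** This also stands. At 10% independent rejection the expected loss is 0.2 of 50. Material losses need common or clustered rejection, and the protocol documents neither.

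**One patient set for both regressions is defensible.** Finger prick values are linked to the DxH800 only through the two regressions in sequence, so a common set has merit. But it can always be reported as a subset, whereas an unscanned tube cannot be recovered.

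**A reader might infer that the filter makes agreement look better than it is.** The protocol does not support that. Its examples of rejection ("rejected due to irregular cell morphology, or microscopically visible hemolysis") illustrate the three-attempt criterion under Exclusion Criteria, not the four-attempt finger prick rule, and it gives no cause for finger prick rejection. Blood that OLO cannot read at all would probably fail the venous scan too and be excluded under the venous rule. The patients regained would mainly be those with capillary collection failures, and nothing shows that they agree less well with the DxH800.

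**A reader might also infer that cytopenic patients are lost most often.** That is plausible, but nothing in the protocol says so.

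**Conclusion.** The point holds as a design flaw of modest and unknown size. The text makes the venous method comparison conditional on finger prick success, nothing in the protocol keeps the affected patients in it, and the missing value cannot be recreated.

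The cost is discarded venous pairs and a selection step irrelevant to the comparison. If rejections are rare and independent, the loss is negligible. The upper figures rest on assumed rejection rates of 30% to 40% per prick or on clustering within patients. The direction of any bias is unknown, and no shortfall in Table 1 numbers is claimed. The change is worth making because it is cheap and the omission cannot be undone after data collection.

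**What to change.** - **Phlebotomy and Scanning Flow:** run the study venous tube on OLO for every enrolled patient once the finger prick attempts have ended, whether or not two succeeded.
- **Study Requirements:** limit the fewer-than-two-pricks exclusion to regression 1, and keep the venous pair in regression 2. The 2-hour limit is written for four scans, so say that it applies to whichever scans are obtained.
- **Table 1 completion:** count only samples complete for both comparisons. One tally then suffices and the stopping rule is unchanged.
- **Reporting:** give regression 2 for all available venous pairs and again for the patients common to both regressions. Tabulate venous scan success among patients with fewer than two successful pricks.

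**Cost:** a few sentences of text, up to three OLO scans per affected patient under the existing venous repeat rule, and slightly different numbers of pairs in the two regressions. The tube is already drawn, so no patient procedure is added. Some of these tubes may also be rejected. The scan then records a failure that would otherwise go unseen, rather than recovering a pair.

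### The 2-hour limit on all four scans takes in the routine DxH800 scan, so it also limits the lab delay that the time-to-result comparison is meant to observe

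*Protocol*

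**What the plan says.** Under Phlebotomy and Scanning Flow, each patient gives two tubes and two finger pricks. For the finger pricks, "Two consecutive finger prick samples will be collected from the 3rd and 4th fingers", and both are scanned on OLO. After those, "the venous sample (collected previously for the study) will be scanned on OLO". For the other tube, "The second tube will be sent to the lab to be scanned on Beckman Coulter DxH800, as part of the routine procedure".

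Study Requirements sets two time limits side by side: "All four scans will be performed within no more than 2 hours", and "All scans should be performed within 8 hours from phlebotomy". Neither names an analysis to which it is confined, and the DxH800 scan is exempt from neither.

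Turnaround is a stated aim in the Background. The Hypothesis describes the interval from phlebotomy to result as "currently prolonged due to the need to send blood samples from the oncology" centre to the central lab. Statistical considerations then defines the comparison: "The time to result will be compared between the time of first available finger prick results" on OLO and the time at which the routine Beckman Coulter result is available. The text on purposeful sampling removes that later phase from the timing analysis, so only initial-phase patients contribute.

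**The concern.** A short window between scans is sensible for the Passing-Bablok regressions, because paired values should come from blood of similar age. The same patients and the same DxH800 scan, however, also supply the time-to-result comparison, and there the gap between the OLO scan and the lab scan is the thing to be measured. A rule that limits this gap limits the outcome.

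If the routine lab route is sometimes slower than the window allows, a site that follows the rule has three options: hurry the tube through the lab, hold back the OLO scans, or lose the sample. The first shortens the lab time, the second lengthens the OLO time, and the third removes the slowest lab cases. All three shrink the apparent advantage of OLO. The result would then not describe the centre's routine service, which is what the workflow aim asks about.

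**Working it through.** **Step 1: which scans the rule covers.** From Phlebotomy and Scanning Flow: 2 finger prick scans on OLO + 1 venous scan on OLO + 1 venous scan on DxH800 = 4. This reproduces the protocol's own count. Only 3 scans are on OLO, so the count reaches four only with the DxH800 scan.

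**Step 2: what the rule limits.** Measure all times from phlebotomy. Let t be the time of the first OLO scan, L the time of the DxH800 scan, and G = L − t.
- The 2-hour rule gives G ≤ 120 min.
- With the 8-hour rule, L ≤ min(t + 2 h, 8 h). For t = 10 min (assumed), L ≤ 130 min; for t = 30 min (assumed), L ≤ 150 min. The 8-hour limit is the tighter one only if t exceeds 6 h.
- The compared difference is D = G + (DxH800 scan-to-result time − OLO scan-to-result time). The rule limits G but neither scan-to-result time.

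**Step 3: how large the effect could be.** The protocol gives no lab turnaround, so this step is illustration only. Assume that G under routine service is log-normal with median m and log-SD s. Then:
- share over 120 min = 1 − Φ(ln(120/m)/s)
- mean of all gaps = m·exp(s²/2)
- mean of gaps kept = mean of all × Φ(ln(120/m)/s − s) / Φ(ln(120/m)/s)
- mean if late gaps are brought to exactly 120 min (by expediting the tube or delaying OLO) = share kept × mean kept + share late × 120

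Example with m = 90, s = 0.5: ln(120/90)/0.5 = 0.575, so the share late is 1 − 0.718 = 0.282. The mean of all is 90·exp(0.125) = 102 min and the mean kept is 75 min. If late gaps are brought to 120 min, the mean is 0.718 × 75.4 + 0.282 × 120 = 88 min.

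| Median gap (min) | log-SD | Over 120 min | Of 50 samples | Mean, all (min) | Mean if late samples are lost | Mean if late gaps become 120 |
|---|---|---|---|---|---|---|
| 45 | 0.3 | 0.1% | under 1 | 47 | 47 | 47 |
| 45 | 0.5 | 2.5% | 1 | 51 | 49 | 50 |
| 60 | 0.3 | 1.0% | under 1 | 63 | 62 | 63 |
| 60 | 0.5 | 8.3% | 4 | 68 | 60 | 65 |
| 90 | 0.3 | 16.9% | 8 | 94 | 84 | 90 |
| 90 | 0.5 | 28.2% | 14 | 102 | 75 | 88 |
| 120 | 0.3 | 50% | 25 | 126 | 96 | 108 |
| 120 | 0.5 | 50% | 25 | 136 | 84 | 102 |

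The shares and the first two mean columns agree with a simulation of 1,000,000 gaps per row. The last column follows from them by the fourth formula.

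**The case against.** The strongest reply is that the protocol states no truncation. It says when a sample leaves the study: fewer than two successful finger prick scans, a third failed venous attempt, or one of the listed exclusion criteria. None of these concerns timing. A reader might infer that patients with slow lab scans are dropped and that the turnaround comparison is therefore conditioned on its own outcome. The text does not say so, and exclusion remains one of three ways a site might respond. This part of the reply stands.

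A reader might also infer that the lab time is cut off at about 2 hours from the draw. That too goes beyond the text. The limit is on the spread between scans, the draw has its own 8-hour limit, and delay between the DxH800 scan and the released result is not limited at all. Nor does the Hypothesis imply a particular lab delay: it calls the interval prolonged but gives no figure.

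It can also be said that the tube is already described as routine, so expediting it would contradict the protocol. That is true, but it does not remove the difficulty. With a slow lab, routine handling and the 2-hour rule cannot both be met unless OLO is held back. A later analysis plan could decide which samples enter the timing comparison, but it could not undo a hurried tube or a delayed OLO scan.

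Finally, the bias works against OLO, so it could understate a benefit but not create one, and turnaround is introduced as an additional aim after accuracy. Both statements are correct. They limit the seriousness of the point without answering it.

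**Conclusion.** The point holds in a limited form. The 2-hour rule, as written, includes the routine DxH800 scan, and in every conforming sample it holds the gap between the first OLO scan and that scan to 120 minutes or less. If routine lab delay sometimes exceeds this, following the rule pulls the measured turnaround difference towards zero.

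The size cannot be settled from the protocol. Under the assumed log-normal gaps it is negligible at a median of 45 minutes and small to moderate at 60. At a median of 90 minutes it is material if late samples are lost: about 17% to 28% of them, with the mean gap falling by 10 to 27 minutes. If late gaps are instead brought just inside the window, the fall is about 4 to 14 minutes. These figures rest wholly on assumed lab times.

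Only the initial-phase time-to-result comparison is touched. The accuracy regressions are not affected, and the window is reasonable for them.

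**What to change.** In Study Requirements, confine the 2-hour window to the pairs that enter the regressions, and say that the routine tube is not to be expedited, nor the OLO scans held back, in order to meet it. In Statistical considerations, state that every initial-phase patient stays in the time-to-result comparison however late the DxH800 scan is.

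The cost is about one sentence in each section, with no extra samples or staff. The small downside is that the regressions and the timing comparison may rest on slightly different numbers of patients, so each count should be reported.

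### The primary and secondary endpoints are a sampling check and a completion rule, and finger prick CBC values are never regressed directly on DxH800

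*Protocol*

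**What the plan says.** The Background section gives the aim as "performance accuracy of CBC results for finger prick samples across the OLO reportable range, and particularly around relevant medical decision points", with workflow and turnaround time as an additional aim. The Hypothesis section expects equivalence to the DxH800 in samples "covering medical decision points for WBC, HGB, PLT, and NEUT"#, unchanged treatment decisions, and a shorter time to result.

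The two endpoint headings hold different content:

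- **Primary endpoint:** after the first two weeks, "the results will be evaluated to assess the coverage of the predefined range groups". The stated purpose is to plan how long sampling must go on and what is still needed, with purposeful sampling if ranges are missing.
- **Secondary endpoint:** "Once all the predefined range groups are covered, the study will be completed and the results will be analyzed".

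The ranges are assigned "according to Beckman Coulter DxH800 as the reference analyzer" (Inclusion Criteria). Purposeful enrolment also follows the routine DxH800 result of the same day.

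The Study design section sets out two comparisons. One is a matrix study of finger prick against venous blood, both on OLO. For the other, "A method comparison study will compare Sight OLO to Beckman Coulter DxH800 using a venous sample collected into a blood tube". The Statistical considerations section follows this. Its first Passing-Bablok pair is "The mean value given by OLO for the finger prick samples and the value given by OLO for the venous sample"; its second is venous OLO against venous DxH800. It also plans a time-to-result comparison (first finger prick result on OLO against the routine DxH800 result) and a record review of whether decisions would have been the same on OLO results.

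**The concern.** An endpoint should name the quantity by which the study is judged. These two describe how samples are gathered and when gathering stops. Range membership is read from the DxH800, so, apart from failed scans, coverage can be reached whatever the bias of OLO. A report that followed the headings could state that the endpoints were met without a word on accuracy, decisions or time.

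The second part concerns the comparison closest to the main aim. The aim is the accuracy of finger prick results, and the reference is the site's DxH800. The planned regressions approach this in two steps, and neither pairs the finger prick value with the reference value. A reader of two acceptable-looking fits would still lack an interval for the difference that matters when a finger prick result replaces the laboratory result.

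**Working it through.** **1. Aims set against the endpoint headings**

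| Stated aim | Under an endpoint heading? | Related planned analysis |
|---|---|---|
| Finger prick accuracy | No | Finger prick vs venous, both on OLO |
| Equivalence to DxH800 | No | Venous OLO vs venous DxH800 |
| Same decisions | No | Record review; OLO sample type not stated |
| Shorter time to result | No | First finger prick result vs routine DxH800 result |

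So 0 of 4 aims is an endpoint, while all 4 have a related analysis.

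**2. Finger prick against DxH800**

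Of the two regression pairs for CBC values, none is finger prick vs DxH800. Time to result is compared directly. The decision review may also use finger prick results, but the text does not say so. Every patient who completes the study has two finger prick scans, one venous OLO scan and one DxH800 scan. The direct pair therefore exists for all of them, less any measurand invalidated by an analyser.

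**3. What the two fits give together**

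Write finger prick = a1 + b1 × venous OLO, and venous OLO = a2 + b2 × DxH800. At a decision point x, the chained bias is approximately a1 + b1(a2 + b2·x) − x. With zero intercepts the proportional bias is b1·b2 − 1. The protocol gives no bias figures, so these are assumed:

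| Bias per step | Both high | Both low | Opposite signs |
|---|---|---|---|
| 3% | 1.03 × 1.03 − 1 = +6.09% | 0.97 × 0.97 − 1 = −5.91% | 1.03 × 0.97 − 1 = −0.09% |
| 5% | 1.05 × 1.05 − 1 = +10.25% | 0.95 × 0.95 − 1 = −9.75% | 1.05 × 0.95 − 1 = −0.25% |
| 10% | 1.10 × 1.10 − 1 = +21% | 0.90 × 0.90 − 1 = −19% | 1.10 × 0.90 − 1 = −1% |

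Chaining thus yields a point value.

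**4. Why it yields no interval**

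Let F, V and D be the finger prick mean, venous OLO and DxH800 values for one patient. Then (F − V) + (V − D) = F − D, and V drops out. If the measurement errors are independent, F − D has error variance σF² + σD². Adding the error variances of the two steps as if they were unrelated gives σF² + 2σV² + σD². The shared scan links the two steps, so their separate intervals cannot simply be combined. This is shown for plain differences; the same sharing affects the two Passing-Bablok fits.

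**5. Time stamps**

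The worksheet records phlebotomy time, the time of the first OLO result, and the DxH800 scanning time. The planned comparison uses the time at which the DxH800 result is available. If scanning time stood in for it, the interval from scan to result would be left out and any gain from OLO understated. The protocol gives no figure for that interval.

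**6. Sample mix**

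The plan is about 30 abnormal plus 20 normal samples, 30 + 20 = 50, which matches the stated total. The abnormal share is 30/50 = 60% by design. Table 1 asks for 2 samples with NEUT# below 0.5 (2/50 = 4%) and 4 with PLT below 18 (4/50 = 8%).

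**The case against.** The strongest case is that the two headings mean milestones: the end of the first phase and the end of the study. On that reading the fault is a label, and the secondary text itself calls for analysis, which the Statistical considerations section supplies. This is a fair reading, and it is right that no aim is left without a planned measure. But renaming the headings would leave the protocol with no endpoint at all, and would not add the missing comparison.

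The two-step design is also deliberate. It separates a specimen effect from an analyser effect, and the hypothesis of equivalence speaks of OLO without specifying finger prick. That stands: omitting the direct fit is not a contradiction. It does leave the main aim without its most direct analysis.

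Four stronger readings are tempting and are not supported:

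- *Finger prick is never compared with DxH800.* Time to result is compared directly, and the decision review may be.
- *The aims go unanalysed.* All four have a related analysis.
- *The two fits hide the total bias.* Read together they give a point value; only its interval is missing.
- *The lack of a ranking among analyses, or of an equivalence margin, is a defect of this protocol.* These are commonly settled in a statistical analysis plan, which is not shown.

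The counts in the lowest ranges do not by themselves fix the precision at those cuts either, because a Passing-Bablok fit uses all pairs.

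**Conclusion.** The point holds in this form and should be fixed. Both endpoint headings contain sampling and completion rules set by DxH800 values, so none of the four aims is an endpoint. For CBC values, 0 of 2 regression pairs sets finger prick against DxH800, although both values exist for each completed patient. The planned fits allow a chained point value of total bias but give no confidence interval for it.

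The chaining figures (for example +10.25%, −9.75% or −0.25% for 5% per step) are illustrations that assume proportional bias and zero intercepts. They show the possible size and do not predict how OLO will perform. The finding about the headings and the pairs rests on the text alone and needs no assumption.

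**What to change.** 1. Move the coverage check and the completion rule to the sampling procedure.
2. **Primary endpoint:** bias of finger prick OLO against DxH800, with 95% CI from a Passing-Bablok fit, for WBC, HGB, PLT and NEUT# at decision points listed in advance. Use the mean of the two finger pricks. Also report the first successful finger prick alone, because that is the single result available in use and the mean of two will scatter less.
3. Keep the two planned regressions as supporting analyses that show whether a bias comes from the specimen or the analyser.
4. **Secondary endpoints:** (a) the decision review, stated to rest on the first finger prick result and to apply to the enriched mix (about 60% abnormal), not to the clinic population; (b) the paired time-to-result difference in the initial phase only, since the protocol already leaves purposeful samples out of the time analysis.
5. Add to the worksheet the time at which the DxH800 result becomes available.

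The cost is 4 measurands × 2 versions (mean and first prick) = 8 more fits, one more recorded time, and an agreed list of decision points. No further blood sample or scan is needed. Precision at the lowest cuts will probably be limited, so the study may support only an estimate there.
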